### Research objectives:

1. To conduct a comparative assessment of the dynamics of nutritional deficiency and nutritional status of patients operated on for malignant tumors of the hepatopancreatoduodenal zone in the early postoperative period during isolated enteral, isolated parenteral and mixed types of nutritional support.
2. To analyze the dynamics of the state of protein and carbohydrate metabolism, the consistency of liver function in cancer patients operated on for malignant tumors of the hepatopancreatoduodenal zone, against the background of isolated enteral, isolated parenteral and mixed type of nutritional support in the early postoperative period.
3. To determine the degree of effectiveness of these methods of nutritional support in this category of patients based on the totality of the results of assessing nutritional status and the dynamics of the level of basal metabolism in these patients in the early postoperative period.

Researched 91 patients, will be divided into 3 groups:

1. The first group (n=31) included patients who received enteral nutrition (EN) after surgery.
2. The second group (n=30) included patients receiving parenteral nutrition (PN).
3. The third group (n=30) receiving mixed nutrition (MN), as is commonly considered the method of partial parenteral nutrition, in the early postoperative period.

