## **Methods of statistical data analysis**

All patients hospitalized for special treatment with a verified diagnosis of a malignant neoplasm were subjected to the study in the abdominal department of the KGP at the Regional Oncological Dispensary, Karaganda.

The quantitative and qualitative indicators obtained during the study were analyzed using descriptive and analytical statistics methods. For statistical processing of qualitative (diagnosis codes, dichotomous data) and quantitative variables: symptom intensity, severity, frequency of occurrence, we used the calculation of the median level (Me) with 25%-75% quartiles (Q25; Q75) and the calculation of the arithmetic mean (M) with error (m) and 95% confidence interval (95% CI), standard deviation (s). Quantitative variables were checked for normality of distribution using the Kolmogorov-Smirnov test, as well as the module of Skewness and Kurtosis for quantitative variables  $| \leq 2 |$ . Differences in the 3 groups of patients for quantitative variables corresponding to a normal distribution were identified using the Student's t test for unrelated groups, first for 3 or more groups, and then in pairs for each pair using the Student's t test. Differences for rank variables, or quantitative but not normally distributed for unrelated groups, were determined by the Kruskal-Wallis test or median test for 3 groups, and then pairwise or non-parametric Mann-Whitney test for each of the 3 pairs (groups 1 and 2, groups 1 and 3, groups 2 and 3), and for related groups (dynamic observations) by the Kendall test for 3 groups and then by the Wilcoxon test (Wilcoxon) for each of the 3 pairs (baseline, after 5 days and after 10 days).

Correlation was performed for quantitative variables according to Pearson and for rank variables according to Spearman. Statistical processing of the results was carried out using the Statistica program version 10.

**Results and discussion.** The nutritional status of patients in all three groups before surgery and during the 10-12 days of the postoperative period according to the methods of assessing nutritional status NRS, SGA and NRI was assessed as normal, moderate and severe malnutrition

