As can be seen from the presented data, in the preoperative period, according to the SGA assessment, 24 patients in the enteral group, 19 patients in the parenteral group, and 17 patients in the mixed group had normal nutritional status before surgery, with variations relative to patients with moderate to severe malnutrition. Assessment of nutritional status before surgery using the NRI scale allowed us to confirm the nutritional status of the vast majority of patients in all groups as relatively normal

Thus, in 62 of the 91 patients examined, the NRI was assessed as true negative (normal nutritional status), in 26 as true positive (moderate malnutrition), and in 3 as severe malnutrition. Data from the NRI method during this time period had a strong correlation with the results of the SGA scale ( $p < 0.005$ ).

On the 10-12th day of the postoperative period in patients of the “enteral” group, the results of the assessment on the SGA scale remained unchanged; according to the NRI rating scale, there was an increase in “moderate malnutrition” per patient (25%).

With parenteral nutritional support, 17 patients had “normal nutrition”, 14 patients had moderate malnutrition, with regression of “severe malnutrition” in 1 patient. In the mixed nutrition group, there was a complete elimination of signs of “severe malnutrition” by 100% according to the given scales ( $p < 0.005$ ).

In patients of all study groups, throughout the entire period of nutritional support, fluctuations in the level of basal metabolism were observed in average values of  $335.89 \pm 53.6$  kcal/day (13.44%) from the initial value - 1-2 days of the postoperative period and were due to variability body mass index and the dynamics of the temperature curve after surgery.

In patients in the groups with enteral and parenteral nutrition, by the end of these types of energy subsidies (days 10-15), the level of basal metabolism was observed to approach its initial values -  $2500.1 \pm 353.4$  kcal/day and  $2350.0 \pm 330.5$  kcal/day days accordingly. With a mixed type of nutrition, there was a statistically significant decrease in the level of basal metabolism by 6.78% ( $2250.0 \pm 105.2$  kcal/s), which allows us to conclude that patients' energy costs are more effectively covered with this option of nutritional support in a comparative aspect with isolated types nutrition ( $p < 0.03$ ).

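### The three-group rank step allows Kruskal-Wallis or the median test with no rule for choosing; on the status scales the median test cannot separate severe from moderate malnutrition

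*Combined protocol and SAP*

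**What the plan says.** The rule is in the report of March 2020, under Methods of statistical data analysis. It covers "Differences for rank variables, or quantitative but not normally distributed for unrelated groups", and says that these "were determined by the Kruskal-Wallis test or median test for 3 groups". Two steps stand beside it. Pairs of arms are compared by the "non-parametric Mann-Whitney test for each of the 3 pairs". Change over time is tested separately, "for related groups (dynamic observations) by the Kendall test for 3 groups and then by the Wilcoxon test". The protocol's own section on data analysis and monitoring names only Student's t-test and Pearson correlation, so it does not settle the choice.

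Status on the screening scales "was assessed as normal, moderate and severe malnutrition", that is, in three ordered classes. Results and discussion gives the baseline picture. By SGA, 24 enteral, 19 parenteral and 17 mixed patients were normal. By NRI, "in 62 of the 91 patients examined, the NRI was assessed as true negative (normal nutritional status"), with 26 moderate and 3 severe. For the mixed arm after surgery, "there was a complete elimination of signs of" severe malnutrition, with p<0.005. The class those patients moved to, and the test behind that p-value, are not given.

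**The concern.** The two permitted tests answer different questions. Kruskal-Wallis uses the full ranking. The median test keeps only which side of the pooled median each patient falls on. If the pooled median of a three-class scale is the best class, the median test merges the other two, and no difference between arms in how severe the malnutrition is can alter it. For a continuous variable it discards all distance from the median, which usually costs power.

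Research objective 1 is a comparison of nutritional status between the three arms, and conclusion 1 of the report favours mixed nutrition over the other two on NRI and SGA. The three-group step bears directly on that claim. With the choice open and no test attributed to any p-value, a reader cannot tell what was compared or reproduce the result.

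**Working it through.** The documents state no alpha, effect size, SD, distribution or power, so there is no planned figure to reproduce. I assume a two-degree-of-freedom chi-square reference at 0.05.

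**1. Where the pooled median falls.** SGA: 24 + 19 + 17 = 60 normal of 91 (65.9%). NRI: 62 of 91 (68.1%). The median is the 46th ordered value, so it is normal on both scales.

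**2. Median test on the SGA counts.** Code normal 0, moderate 1, severe 2. Above the median then means not normal: 31 − 24 = 7, 30 − 19 = 11 and 30 − 17 = 13, total 31. Expected counts are n × 31/91 = 10.56, 10.22, 10.22 not normal, and n × 60/91 = 20.44, 19.78, 19.78 normal.

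Chi-square = Σ(O − E)²/E = 1.200 + 0.060 + 0.756 + 0.620 + 0.031 + 0.391 = 3.06, p=0.217.

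The moderate/severe split does not enter the formula. With reversed coding, splitting at below against at-or-above the median gives the same table.

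**3. Kruskal-Wallis on the same counts.** The SGA split into moderate and severe is not given by arm. As an illustration I put 3 severe cases in the mixed arm (the NRI total for the whole trial) and none elsewhere.

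- Mid-ranks: 60 normal at 30.5, 28 moderate at 74.5, 3 severe at 90.
- Rank sums: enteral 24 × 30.5 + 7 × 74.5 = 1253.5; parenteral 19 × 30.5 + 11 × 74.5 = 1399; mixed 17 × 30.5 + 10 × 74.5 + 3 × 90 = 1533.5. The total is 4186 = 91 × 92/2.
- Uncorrected H = 12/(91 × 92) × (1253.5²/31 + 1399²/30 + 1533.5²/30) − 3 × 92 = 2.519.
- Tie factor = 1 − (215,940 + 21,924 + 24)/753,480 = 0.684.
- Corrected H = 2.519/0.684 = 3.68, p=0.159.

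Varying the assumption:

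| Mixed arm (30 patients) | Median test | Kruskal-Wallis |
|---|---|---|
| 13 not normal, 0 severe | 3.06, p=0.217 | 3.02, p=0.220 |
| 13 not normal, 3 severe | 3.06, p=0.217 | 3.68, p=0.159 |
| 13 not normal, 8 severe | 3.06, p=0.217 | 5.10, p=0.078 |
| 13 not normal, all 13 severe | 3.06, p=0.217 | 6.95, p=0.031 |
| 3 patients moved to normal (10 not normal, 0 severe) | 1.56, p=0.459 | 1.54, p=0.463 |

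The median test is blind to the moderate/severe boundary but does see a move to normal. Kruskal-Wallis sees both, though with 3 severe cases it changes little.

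**4. Power for continuous variables.** Simulated trials with 31/30/30 patients and one arm shifted; 10,000 runs per cell at 0.5 and 0.7 SD, 20,000 at 0.75 SD. Entries are Kruskal-Wallis power, median-test power, and loss in points.

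| Shape | 0.5 SD | 0.7 SD | 0.75 SD |
|---|---|---|---|
| Normal | 46.9%, 31.9%, 15.0 | 77.3%, 58.1%, 19.2 | 82.7%, 64.3%, 18.4 |
| t with 3 df | 75.2%, 68.1%, 7.1 | 96.4%, 92.3%, 4.1 | 97.9%, 95.0%, 2.9 |
| Laplace | 63.9%, 63.4%, 0.5 | 89.7%, 87.2%, 2.5 | 93.3%, 91.2%, 2.1 |
| Shifted exponential | 82.4%, 55.2%, 27.2 | 97.9%, 86.6%, 11.3 | 98.7%, 90.5%, 8.2 |

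The normal row also holds for lognormal data shifted on the log scale, because both tests depend only on ranks. Simulation error is about a point.

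**The case against.** The strongest reply is that the choice hardly matters to what the report concludes, and much of it stands.

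- A reader might infer that the median test hides the very change claimed for mixed nutrition. The documents do not support that. They do not say whether the severe patients became moderate or normal, and a move to normal would be seen. The claim is also worded as change over time within one arm, for which the methods name Kendall and Wilcoxon.
- The pairwise Mann-Whitney step uses full ranks and does separate severe from moderate. Nothing in the text makes it conditional on a significant three-group result.
- With 3 severe cases, Kruskal-Wallis gives p=0.159 against p=0.220 with none, so neither test would show a difference.
- A reader might take a loss of about 20 points as general. It is not. It depends on the distribution and effect size, which the documents do not state, and variables that pass the normality check go to the t-test instead.
- A reader might suspect that the more favourable p-value was chosen. The open choice would permit it, but nothing shows that it happened. Nor does the report say that the median test was used at all, or that status classes rather than scores were analysed at this step.

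These points limit the consequence. They do not supply a rule for choosing, identify the test behind any three-group p-value, or make the median test sensitive to severity among malnourished patients.

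**Conclusion.** The point holds as a minor weakness in the choice of analysis. The three-group rank step is ambiguous, and one of its two permitted tests is poorly suited to the status scales. While normal remains the pooled median class, as it was before surgery, that test cannot register a between-arm difference in severe against moderate malnutrition. For continuous variables it usually has less power: for one arm shifted by 0.5 to 0.75 SD the loss is about 15 to 20 points for normal or lognormal data, about 3 to 8 for t with 3 df, near zero for Laplace and about 8 to 27 for shifted exponential. All of these rest on assumed shapes, shifts and a 0.05 level.

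The pairwise and within-arm tests are not affected. With so few severe cases by NRI, the practical effect on the status result is small.

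**What to change.** Name tie-corrected Kruskal-Wallis as the only three-group test for every rank or non-normal variable and every day. State in the report which test produced each three-group p-value already given. Re-run with Kruskal-Wallis any that came from the median test, and report these as a re-analysis. The study is finished and its methods are written in the past tense, so simply striking the median test from the text would misdescribe the work if it had been used.

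No new data are needed. The cost is a few re-run tests and some added attribution, and possibly slightly less power for a variable with very heavy tails.

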43-87% of patients with malignant neoplasms of various localizations have pronounced disturbances in body composition, which correlate with the prevalence of the tumor process and are aggravated during combined treatment. This is based on disturbances in protein, carbohydrate and fat metabolism caused by the systemic effect of the tumor on the body. Violation of nutritional status has a significant impact on the outcome and prognosis of the disease, inevitably increases the duration and cost of treatment, contributes to an increase in mortality and the number of complications, such as infection, slower wound repair, immunosuppression, hemocoagulation disorders, decreased concentrations of blood plasma proteins and a number of enzymes, metabolic disorders medications, decreased tolerance to surgical treatment, radiation and chemotherapy. BUT. Stadley showed that when depleted patients lost 20% of their initial body weight, mortality after surgery reached 33%, and in non-depleted patients -3.5%. According to B.R. Bistrian, G.L. Blakburn, with a 5% decrease in body weight during hospital stay, the length of stay increases by 2 times, and the frequency of complications increases by 3.3 times. J.L. Mullen and G.P. Buzby (1980) showed that impaired nutritional status in surgical patients leads to an increase in postoperative complications by 6 times, and mortality by 11 times, while timely administration of adequate nutritional therapy to such depleted patients reduces the number of postoperative complications by 2-fold. 3 times, and lethality - 7 times.

In this regard, the importance of accurately assessing the nutritional status of patients is obvious, which is the first step in treating and preventing further progression of malnutrition. A variety of methods are used to assess a patient's nutritional status. The use of enteral nutrition in the postoperative period contributes to the rapid elimination of intestinal paresis, early activation of intestinal motility, improved regeneration of the intestinal mucosa and activation of its absorption function.

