## Report

№ MUK\_NutS-HPD-PO\_2017 from March 17, 2020

Karaganda Medical University

This study was approved by the Karaganda Medical University of the city of Karaganda of the Republic of Kazakhstan. Research and Ethics Committee of February 12, 2020 Protocol №4. All methods were carried out in accordance with ethical principles and rules approved by the ethics committee.

The clinical trial period was started in January 2017 and completed in March 2020

**Purpose of the study:** To improve the nutritional status of cancer patients after operations performed in the hepatopancreatoduodenal zone in connection with malignant neoplasms, through a comprehensive comparative analysis of the effectiveness of isolated enteral, isolated parenteral and mixed type of nutritional support in the early postoperative period.

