### **Conclusion:**

1. According to the NRI nutritional status assessment scales, the SGA mixed type of nutritional support at the time of transfer of patients to the specialized department and upon completion of this area of intensive therapy in the specialized department by 12-15 days of the postoperative period showed higher effectiveness in stabilizing the condition and maintaining the patients' caloric intake in a comparative aspect with the group of isolated enteral nutrition and parenteral nutrition.
2. Throughout the entire period of isolated enteral, parenteral and mixed nutritional support, all patients (100%) showed a relatively constant level of total blood protein.
3. In patients of all three groups, throughout the entire period of nutritional support, fluctuations in the level of basal metabolism were observed, which was due to the variability of body mass index and the dynamics of the temperature curve after surgery. In patients in the groups with enteral and parenteral nutrition, by the end of nutritional support (days 15-20), the level of basal metabolism was observed to approach its initial values. With a mixed type of nutrition, a statistically significant decrease in the level of basal metabolic rate was observed, which suggests a more effective coverage of the energy costs of patients with this option of replenishing nutritional ingredients.

**Researcher:** [name], PhD student KSMU

[contact].

e-mail: [contact].

[figure not shown]
Signature  17.03.2020

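### Conclusion 1 ranks mixed feeding first on SGA and NRI without allowing for a baseline SGA difference that gave the mixed arm more room to improve than the enteral arm

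*Combined protocol and SAP*

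**What the plan says.** The report (Research objectives) describes three arms: "The first group (n=31) included patients who received enteral nutrition (EN) after surgery", then parenteral and mixed arms of 30 each. Nutritional status was graded before and after surgery as normal, moderate or severe malnutrition.

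Under Results and discussion, the baseline SGA result is that "24 patients in the enteral group, 19 patients in the parenteral group, and 17 patients in the mixed group had normal nutritional status". NRI at baseline is given only for the whole study: "in 62 of the 91 patients examined, the NRI was assessed as true negative (normal nutritional status", with 26 moderate and 3 severe.

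At days 10-12 the report describes the arms in different terms:

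- **Enteral:** no change on SGA; on NRI, one more moderately malnourished patient, labelled 25%.
- **Parenteral:** 17 normal and 14 moderate, with one severe case resolved; the scale is not named.
- **Mixed:** the severe category emptied on the scales used, with p < 0.005; no patient count is given.

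Conclusion 1 then says that mixed feeding, judged on NRI and SGA, "showed higher effectiveness in stabilizing the condition and maintaining the patients' caloric intake" compared with the two isolated routes.

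Methods of statistical data analysis lists between-arm tests (Student's t, Kruskal-Wallis or median test, Mann-Whitney) and within-arm tests over time (Kendall, Wilcoxon). None adjusts for baseline category or is stratified by it.

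**The concern.** On a three-category scale, a patient who starts at normal can only stay there or get worse. Only patients who start malnourished can show improvement. If one arm holds a larger share of them, it will tend to show more improvement even when the feeding routes work equally well.

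That is the situation between the mixed and enteral arms on SGA. Conclusion 1 takes no account of it and sets side by side results that describe different starting populations. At stake is whether the stated advantage of mixed feeding reflects the route or the patients who happened to be in that arm.

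**Working it through.** **Reproducing the report's own total.** NRI at baseline: 62 + 26 + 3 = 91, which matches the arm sizes 31 + 30 + 30 = 91. On NRI 62/91 = 68.1% were normal. On SGA 24 + 19 + 17 = 60, and 60/91 = 65.9%.

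**Room to improve on SGA** = (arm size − normal before surgery) / arm size:

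| Arm | n | Normal | Malnourished | Share |
|---|---|---|---|---|
| Enteral | 31 | 24 | 7 | 22.6% |
| Parenteral | 30 | 19 | 11 | 36.7% |
| Mixed | 30 | 17 | 13 | 43.3% |

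**Mixed-to-enteral ratio.** (13/30)/(7/31) = 1.92. Standard error of the log ratio = √(1/13 − 1/30 + 1/7 − 1/31) = 0.393. The 95% CI is 1.92 × exp(±1.96 × 0.393), or 0.89 to 4.14. Fisher's exact test, enteral against mixed, gives p = 0.106; chi-square across three arms gives p = 0.217.

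**Direction of the bias.** Suppose that, in every arm, a malnourished patient moves up with the same probability q and a normal patient worsens with the same probability w. The net improved share in an arm with malnourished share m is q·m − w·(1 − m). Mixed minus enteral is then (q + w) × (0.433 − 0.226) = (q + w) × 0.208. This is positive for any q or w above zero, with no effect of route. It shows direction only: q and w are unknown, and the outcome reported for the mixed arm is loss of the severe category, not movement up by one category.

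**Why the size cannot be computed.** Room to empty the severe category depends on the number of severe patients in each arm. The report text gives 3 on NRI for the whole study and no split. The counts 7, 11 and 13 pool moderate and severe.

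**NRI by arm.** No split is given. If the 25% for one enteral patient means 1 added to 4 moderate cases (an assumption), and the enteral arm held 0 to 3 of the severe cases, then 4 to 7 of 31 enteral patients (12.9% to 22.6%) were malnourished, against 25 to 22 of 60 in the other two arms (41.7% to 36.7%). The direction is the same, but it rests on that reading.

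**Parenteral follow-up.** 17 + 14 = 31 in an arm of 30. If the scale is SGA, the number normal fell from 19 to 17 although 11 patients had room to improve.

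**The case against.** Several parts of the case for leaving Conclusion 1 alone are sound.

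- **Chance.** The imbalance rests on 13 patients against 7, and the interval includes 1. That is true, but it answers a different question: an observed difference in a prognostic baseline distorts an unadjusted comparison whatever its p-value.
- **Parenteral arm.** It does not follow the room-to-improve pattern. This stands: baseline case mix does not explain all the results, and the bias argument applies to mixed against enteral.
- **Ceiling.** It exists only on the three-category scale. BMI, total protein, albumin, transferrin and lymphocytes were also assessed, and normally nourished patients are informative about stabilisation. This also stands. But unchanged SGA in the enteral arm is itself stability, so it does not support ranking that arm lower.
- **Missing display.** The results text refers to presented data. If a table gave categories by arm, the size of the problem could be worked out from it.

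A reader might also infer more than the documents support:

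- **That entry without a nutritional criterion caused the problem.** Admitting all comers does not make arms differ. The difference arises from how patients reached the arms. Protocol section V describes random selection of patients, and no allocation to arms is described. The protocol's purpose and the report's hypothesis are also not confined to correcting malnutrition.
- **That the sample was unusually well nourished.** The introduction's "43-87% of patients with malignant neoplasms of various localizations have pronounced disturbances in body composition" concerns another measure and a wider population, so it is no benchmark for SGA or NRI here.
- **That the mixed-arm advantage is wholly an artefact of a known size.** Without severe counts by arm, no size can be given.

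In the other direction, p < 0.005 for the mixed arm might be read as proof of superiority. The report does not tie it to a between-arm contrast.

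**Conclusion.** The point holds. Conclusion 1 rests on unadjusted whole-arm and within-arm results in arms whose baseline SGA differed: 22.6%, 36.7% and 43.3% of enteral, parenteral and mixed patients could improve. The mixed-to-enteral ratio is 1.92 (95% CI 0.89 to 4.14), compatible with chance.

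Comparison of improvement between mixed and enteral feeding is biased towards mixed feeding. The direction follows from the SGA counts, on the assumption that patients of the same baseline category have the same prospects in each arm. The size is not computable from the report. The documents show that the claimed advantage could arise this way, not that it did. They do not support a ranking of the routes on SGA and NRI as Conclusion 1 states it.

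**What to change.** The report gives the trial as completed in March 2020, so the remedy lies in analysis and wording.

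1. Reconcile the parenteral follow-up counts (31 in an arm of 30) and name the scale they refer to.
2. For each arm and each scale, report a table of category before surgery against category at follow-up, with counts.
3. Show correction among patients malnourished before surgery (SGA denominators 7, 11 and 13) separately from maintenance among those normal before surgery (24, 19 and 17).
4. Compare the arms with stratification by, or adjustment for, baseline category, and give confidence intervals.
5. Reword Conclusion 1 to claim superiority of mixed feeding on SGA or NRI only if that comparison supports it. Otherwise, state that the data do not distinguish the routes.

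The cost is a small set of tables and one model or stratified test, using data already recorded. The downside is precision. Among malnourished patients, even if none of the 7 enteral patients improved, at least 7 of the 13 mixed patients (54%) would have to improve for a two-sided Fisher p below 0.05; 6 of 13 gives about 0.051. For that reason interval estimates should carry the conclusion, and it will probably be weaker than the present one.

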A comparative analysis of the dynamics of ALT and ASAT values in all patients in the study groups on the 2-3, 6-8, 10-12 days of the postoperative period reflected an excess of their normal values after surgery in some patients tens of times in the first day of the postoperative period. These changes can be explained, first of all, by the surgical intervention itself and its volume, the underlying disease of the hepatopancreatoduodenal zone and the associated cytolytic syndrome against the background of cholestasis [9,10,11].

In terms of assessing the dynamics of blood transaminase levels, in the majority of patients in the first group (78.2%), by the 5th and 10th days there was a decrease in ALT and AST values, on average, by 32.1 and 40.15%, respectively.

In the overwhelming number of patients in the second group (81.6%,  $n=26$ ), a statistically significant decrease in the level of these blood transaminases was also recorded, on average by 72.2% by the fifth day and 66.7% by the 10th day of the postoperative period from level of their initial indicator.

With a mixed type of nutritional support, by the 5th day of the postoperative period, the average significant decrease in transaminases was, on average, up to 72.6% of the initial values ( $p = 0.000$ ); by the 10th day of the postoperative period, their level decreased to 63.8% from the previous achieved value of 5 days ( $p=0.008$ ).

When comparing analyzes of the level of total blood bilirubin in patients of all nutrition groups, there was a strong direct correlation with a decrease in the level of blood transaminases, which, apparently, was also due to the creation of sufficient intraoperative bile outflow due to drainage of the biliary tract and elimination of the cause of obstructive jaundice (tumor).

However, high values of total blood bilirubin that persisted on the first day after surgery were due to temporary swelling of the biliary tract, which caused the excess of the norm by more than 10 times ( $p = 0.000$ ).

On days 5-7, there was a tendency towards a 5-6 fold decrease in its level from the initial values, which gradually decreased to normal values by days 10-12 and in some patients persisted until discharge from the hospital ( $p = 0.004$ ).

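### The parenteral-arm figures do not fit the stated 30 patients: 17 + 14 = 31 if taken on one scale, and 26 patients are printed as 81.6% where 26/30 is 86.7%

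*Combined protocol and SAP*

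**What the plan says.** The protocol (section II, Number of participants) and the report (Research objectives) give the same arm sizes. In the report the total is "Researched 91 patients, will be divided into 3 groups", and the arms are "The first group (n=31) included patients who received enteral nutrition (EN) after surgery", "The second group (n=30) included patients receiving parenteral nutrition (PN" and "The third group (n=30) receiving mixed nutrition (MN".

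The results text follows the report's heading Methods of statistical data analysis. It describes nutritional status on NRS, SGA and NRI in three grades: normal, moderate malnutrition and severe malnutrition. On SGA before surgery it gives "24 patients in the enteral group, 19 patients in the parenteral group, and 17 patients in the mixed group had normal nutritional status before surgery". For the parenteral arm at days 10-12 it gives "With parenteral nutritional support, 17 patients had “normal nutrition”, 14 patients had moderate malnutrition, with regression of “severe malnutrition” in 1 patient", without naming a scale.

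The transaminase paragraphs of the same section report a decrease in enteral patients as "in the majority of patients in the first group (78.2" per cent, with no count. For the parenteral arm they give a percentage and a count together: "In the overwhelming number of patients in the second group (81.6%, $n=26".

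The report's Conclusion 1 places mixed support above both enteral and parenteral support on NRI and SGA, at transfer and by days 12-15.

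**The concern.** Normal, moderate and severe are exclusive grades, so on any one scale and at any one visit their counts cannot exceed the arm size. Read in the ordinary way, the parenteral sentence breaks that rule. A second parenteral figure, on a different outcome, pairs a count and a percentage that do not belong together for an arm of 30.

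Objective 1 is the comparative course of nutritional status, and Conclusion 1 is its answer. The 17/14 sentence is the only postoperative SGA or NRI distribution for the parenteral arm in the text. If it cannot be tied to a scale and a denominator, neither the change within that arm nor its contrast with the mixed arm can be worked out from what is printed. The transaminase figures belong to objective 2. They bear on how reliable the denominators are in general, not on the nutritional-status course.

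**Working it through.** **Inputs.** Arm sizes 31, 30 and 30 (protocol section II; report, Research objectives). Parenteral days 10-12: 17 normal, 14 moderate, 1 with regression of severe malnutrition. Parenteral SGA normal before surgery: 19. Transaminase decrease: 26 patients and 81.6% (parenteral), 78.2% (enteral). All results are from the report's results text.

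**Totals that agree.** Arms: 31 + 30 + 30 = 91. NRI before surgery, all arms: 62 + 26 + 3 = 91. The declared sizes are therefore consistent with each other and with the baseline NRI count.

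**Parenteral grades at days 10-12.**
- 17 + 14 = 31, against 30.
- If the one patient with regression is a further patient, and not already among the 17 or 14, the sum is 32.
- With 17 normal, at most 30 − 17 = 13 patients can be moderate or severe.
- Missing assessments would lower the sum, so they cannot produce a surplus.

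**Comparison with baseline, assuming 17/14 is SGA.** Before surgery 19 were normal, leaving 30 − 19 = 11 malnourished. Normal patients then fall by 19 − 17 = 2, and moderate patients rise by at least 14 − 11 = 3. A one-patient surplus is of the same order as these changes.

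**Parenteral transaminase figure.**
- 26/30 = 86.7%; 26/31 = 83.9%; 26/32 = 81.25%. With one patient missing, 26/29 = 89.7%, which is further away.
- 0.816 × 30 = 24.5 patients. The nearest whole counts give 24/30 = 80.0% and 25/30 = 83.3%.
- Among all whole-number fractions with denominators below 60, only 31/38 and 40/49 round to 81.6%. No denominator of 37 or less does, so missing patients cannot account for it.

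**Enteral transaminase figure.** 0.782 × 31 = 24.2. The nearest whole counts give 24/31 = 77.4% and 25/31 = 80.6%. Among denominators below 60, only 43/55 rounds to 78.2%, so missing patients do not explain this one either.

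**The case against.** **The counts may come from two scales.** The sentence names none. The sentence before it treats SGA and NRI separately, and the next refers to scales in the plural. The scales do differ: before surgery 24 + 19 + 17 = 60 patients were normal on SGA and 62 on NRI. If 17 and 14 come from different scales, they need not add to 30. This stands as a possibility, so the sum cannot be called impossible without the one-scale condition. It does not rescue the sentence, which reads as one classification. On this reading the text gives no complete postoperative parenteral distribution for either scale.

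**Percentages may be of readings, not patients.** Two enzymes at two visits in 31 enteral patients give 31 × 4 = 124 readings, and 97/124 = 78.2%. The report says patients, so this is only an assumption. It means that 78.2% is ruled out as a share of 31 patients, not under every conceivable definition.

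**The figures may be given correctly elsewhere.** The results text refers to presented data that our copy does not show. A table there could hold the right counts, but the printed sentence would still have to be brought into line with it.

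**The effect may be small.** If one count is off by one, the scale is SGA and nobody remains severe, the arm is 17/13 or 16/14. Normal is then 56.7% or 53.3%, against 19/30 = 63.3% before surgery, and the direction does not change. The statement that severe malnutrition disappeared in the mixed arm does not use the parenteral counts. Both points stand.

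**Stronger readings a reader might infer.** One is that patients were counted in an arm other than their own after a change of feeding route. No section reports a crossover or a reassignment, and if two scales were mixed the arm would still be 30. Another is that the arm really held 32, because 17 + 14 + 1 = 32 and 26/0.816 = 31.9. But 26/32 is 81.25%, not 81.6%, and 31 + 32 + 30 = 93 breaks the total of 91 unless another arm is smaller. A misprinted percentage fits as well. Nor does the 26 itself exceed the arm.

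**Conclusion.** The point holds in limited form. If 17 and 14 come from one scale, the parenteral arm is over-counted at days 10-12 by one patient, or by two if the regressed severe case is separate. If they do not, the sentence mixes scales without saying so. Independently, the 26 and the 81.6% cannot both describe an arm of 30: the percentage is about 5 points below 26/30 and matches no whole count out of 30. The enteral 78.2% matches no whole number of patients out of 31. These last two results assume that the percentages are shares of patients, as the report words them.

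The documents do not show which element is at fault: the counts, the percentages, the scale or the arm size. The consequence is confined to the parenteral comparison in Conclusion 1, which cannot be checked from the text, and to the reported transaminase proportions under objective 2. The mixed-arm result is not refuted by this, and no change in arm membership has been shown. The fault lies in the reported results, and it should be corrected before the parenteral comparison is relied on.

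**What to change.** 1. Reconcile the parenteral arm size and every count with the patient-level data.
2. Print a table by arm and separately by scale, with normal, moderate, severe and missing before surgery and at each postoperative assessment. Each row should sum to 31, 30 or 30, or to that number less a stated number missing.
3. Correct the 17/14 sentence and name its scale. Correct 81.6% and 78.2%, giving numerator and denominator for each and saying whether the unit is a patient or a reading.
4. Restate the parenteral comparison in Conclusion 1 according to the corrected counts.

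The cost is a recount of data already collected and one added table. The drawback is that Conclusion 1 may come out weaker.
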